11.5. Implant Procedure (Day 0; required); Re-implant/Revision Procedures (as needed)

Subjects that meet all of the entry criteria and consent to the procedure are eligible. All subjects will be implanted, per center SOC procedure, with one of 3 Rally CRT-P models; selection of subject appropriate device will be at the discretion of the Investigator based on appropriate medical considerations. All future follow-ups will be based on this date.

Subjects that need re-implant or revision procedures, as determined by the Investigator, will undergo the same procedures as described for Day 0. The reason for re-implant/revision is to be documented in the eCRF.

While the Investigator should follow the center's SOC procedures and the IFU, it is important to ensure that the pulse generator has good contact with the surrounding tissue of the implantation pocket, and then suture it in place to minimize device migration (Figure 5-2).

In addition, two strategies are recommended for device configuration and programming:

- 1) Non-apical, non-septal-pacing vector, AV optimization, Echocardiographic optimization, QLV optimization any acceptable pacing threshold and no PNS
- 2) Non apical pacing vector, no further optimization, good pacing threshold and no PNS.

All standard lead/device components are to be assessed during and/or after implant.

The following data elements will be captured DURING the index procedure:

- Procedure time skin to skin, number of LV lead repositioning attempts
- Model and serial number of all implanted and active devices
- Final LV pacing configuration: impedance and threshold
- Final sensing configuration LV-R-wave
- Artifacts during sensing post-implant (ADE reporting)
- Confirmation /assessment of MICS, lead insertion, header
(all lead insertion difficulties or ball seal problems (including but not limited to: missing springs, dislodged springs, etc.) must be reported as an event. The subject impact should be documented in the event description.
- Bipolar sensing amplitude for right atrial (RA) and right ventricle (RV) electrodes should be measured and recorded
- Occurrence of any device-related event (unanticipated serious adverse device effect [USADE], ADE, DD) or SAEs unrelated to the device

The implant procedure will be noted in the eCRF as intended, attempted or successful.

MICS should be used for any device interrogation. Any DDs (including but not limited to: drop-outs during use of MICS, threshold test taking too long, loss of STAT Pace, etc.) are to be reported. The subject impact should be documented in the event description.

Details on the occurrence of any USADE, SADE, ADE, DD, SAE or device-related malfunction are to be recorded.

Implant data shall be documented as indicated in Table 11-2 and Table 11-3.

Table 11-2: Implant Procedure Assessments

Pacing configuration	Pacing Threshold at 0.5 ms*	Impedance In Ω	Sensing Amplitude
E1 – unipolar (PSA)			
E2 – unipolar (PSA)			
E3 – unipolar (PSA)			
E4 – unipolar (PSA)			
Final minimum measurements after pocket closure			
Final RA lead measurements			
Final RV lead measurements			
Final LV – lead configuration E... to			

* 0.4 can be used as a standard setting, per Investigator discretion; to be documented in the eCRF
 eCRF=electronic Case Report Form, LV=left ventricle, PSA=Pacing System Analyzer, RA=right atrium

Table 11-3: Post-pocket Closure Sensing Assessments

Sensing Configuration V – V During Smart Delay with Pacing Configuration	V-V timing in ms
E1	
E2	
E3	
E4	

The POST function is to be switched on POST-IMPLANT for device interrogation. Confirmation of all measurements via POST will be noted in the eCRF, with follow-up manual confirmation of:

- pacing threshold for all 3 electrodes
- pacing threshold of at least 3 of the possible 17 LV vectors per configuration on unipolar, bi-polar and extended bipolar
- impedance for all 3 electrodes
- intrinsic signal (p-wave, r-wave)
- all vectors of LV lead.

A DD report is to be submitted for any parameter that does not function appropriately.

11.6. Pre-discharge Clinic Visit (0-5 days post-implant procedure; required)

A device assessment will be performed in order to document the proper device function and any adverse device events or SAEs that may have occurred since the implant procedure. Current medication classes prescribed shall be documented, and device interrogation performed according to SOC practices.

At this visit, a BiV-paced post-implant 10s programmer ECG recording is required to be uploaded to the study database for core lab review (should be manually measured as SOC). Channels to be used include:

- RA (RAS/RAP)
- RV (RVS/RVP)
- LV (left ventricular sensed event [LVS]/left ventricular pressure [LVP])
- surface ECG.

In general, device based measurements at this visit are to include the PR interval over multiple intervals; RVS to LVS timing for each LV electrode; thresholds; and impedances and amplitude measurement.

In addition to all automatic POST measurements, manual testing should be done of all leads (impulse, threshold, sensing amplitude) and output programming. All out of range alerts from POST should be documented on the event page regardless of the direct subject impact. Any subject impact is also to be documented in the event description.

[figure not shown]
Output programming should be tested via LVAT and manually, the functionality of MICS confirmed and the PRM interface rating is to be documented. Pre-discharge device assessments as noted in Table 11-4, Table 11-5 and Table 11-6 are to be documented.

Device programming (Figure 11-1) should include selection of final LV pacing/sensing vectors; Smart delay should be used to determine paced and sensed AV delays and

confirmation of LV-RV offset. All subjects are to be programmed to a non-rate adaptive pacing mode from the time of discharge until the 1 month follow-up visit (e.g., DDD). Accelerometer and/ or MV Sensor might be programmed ON for subjects *with previous device implants (e.g., pacemaker) with a known need for rate adaptive pacing*. If a rate adaptive pacing mode is programmed, reasons must be documented in the eCRF. Pacing Rate and AV delay should be programmed at the physician's discretion so that subjects receive a maximum of ventricular pacing rate to assure optimal CRT therapy.

To obtain an accurate MV baseline, the MV sensor will be calibrated automatically or can be calibrated manually. A new, manual calibration should be performed if the pulse generator is removed from the pocket following implant, such as during a lead repositioning procedure, or in cases where the MV baseline may have been affected by factors such as lead maturation, air entrapment in the pocket, pulse generator motion due to inadequate suturing, external defibrillation or cardioversion, or other patient complications (e.g., pneumothorax).

Figure 11-1: Pre-Discharge Programming Screen

The LATITUDE data collection system will be set up at discharge (± 5 days). A weekly interrogation frequency should be programmed until 3 month follow up. After 3 month follow up the interrogation might be less frequent but not less than monthly. Inability to set up or program the data collection system will be considered a CIP deviation.

After the final programming (DDD pacing mode) and setting rate adaptive pacing (MV sensor) to “passive”, the final data interrogation must be saved as data file and stored in the subject binder. The file should be uploaded as a ZIP file into the study database.

Additional details to be documented in the eCRF:

- final LV pacing vector
- SMART delay optimization used (YES/NO)
- programmed AV delay
- how accelerometer was programmed at the end of pre-discharge (ON/Passiv)
- how MV sensor was programmed at the end of pre-discharge (ON/Passiv)
- programmed pacing mode

All information is to be saved to a disc at the end of the visit.

XL and MV sensors should be in the passive mode.

Chronotropic incompetent subjects (e.g. rate trend shows all time < 100 bpm) may receive benefit from the use of available rate response functions.

All current/concomitant heart failure medication classes (Beta blockers, angiotensin-converting-enzyme [ACE] inhibitors, diuretics, etc.) at baseline and at time of discharge are to be noted in the eCRF; any changes made to these medications during hospitalization are also to be noted in the eCRF.

Details on the occurrence of any USADE, SADE, ADE, DD, SAE or device-related malfunction which have occurred since the implant procedure are to be recorded.

Table 11-4: Pre-discharge Device Assessments

Pacing configuration	Pacing Threshold at 0.5 ms	Impedance in Ω
E1 – unipolar (Can) (device based)		
E2 – unipolar (Can) (device based)		
E3 – unipolar (Can) (device based)		
E4 – unipolar (Can) (device based)		
E1 – Ext Bipolar (device based)		
E2 – Ext Bipolar (device based)		
E3 – Ext Bipolar (device based)		
E4 – Ext Bipolar (device based)		
Bipolar E1 → E2 (device based)		
Bipolar E1 → E3 (device based)		
Bipolar E1 → E4 (device based)		
Bipolar E2 → E3 (device based)		
Bipolar E2 → E4 (device based)		
Bipolar E3 → E2 (device based)		
Bipolar E3 → E4 (device based)		
Bipolar E4 → E2 (device based)		
Bipolar E4 → E3 (device based)		
RV Threshold (bipolar)		
RV Threshold Unipolar (optional)		
RA Threshold (bipolar)		
RA Threshold Unipolar (optional)		

Table 11-5: Pre-discharge Sensing Assessments

Sensing Configuration V – V during Smart Delay with Pacing Configuration		V-V timing in ms
E1		
E2		
E3		
E4		

Table 11-6: Sensing Configuration

LV Sensing Configuration	R-Wave in mV
LV - E1	
LV - E2	
RV Sensing	
RA Sensing	

11.7. 1 Month Clinic Visit (30 ± 15 days post-implant procedure; required)

Clinical assessments may be done at this visit, if the assessment is part of the center's SOC procedures. All subjects are to be programmed to a non-rate adaptive pacing mode until this visit.

Prior to the initial device interrogation, subjects will do a 6 minute brisk walk, in a non-rate adaptive pacing mode. Data to be collected in association with the walk include:

- age predicted maximal heart rate
- heart rate prior to and at the conclusion of the walk
- maximum heart rate
- distance walked (in meters)
- any symptoms experienced.

All subjects shall be “interrogated” after the 6 minute walk test and the data must be saved prior to any re-programming.

Chronotropic incompetent subjects (e.g., rate trend in the device for the previous 24 hours [including the 6 minute walk test] shows all time < 100 bpm) may receive benefit from the use of MV sensor.

If, after the walking test, the maximum heart rate is < 100 bpm or < 80% of the age predicted heart rate ($[220\text{-age}]*80\%$), the MV sensor should be programmed on (e.g., DDDR); the maximum sensor rate should be at 80% of the age predicted maximal heart rate (APMHR).

The accelerometer should be programmed to “Passiv” during the course of the study until the Latitude close out follow up. In case the accelerometer needs to be turned on for clinical reasons an event and corrective action need to be documented in the study database.

Rate adaptive pacing during this study should be triggered by the MV Sensor only.

Subjects with a maximum heart rate < 80% of their respective age predicted maximum ($[220\text{-age}]*80\%$) after the 6 minute walk will receive sensor optimization, per the Optimization Guidelines:

- The maximum sensor rate should be programmed to: APMHR * 80% (Table 11-7)
- The maximum sensor rate should not be programmed below 110 bpm
- The programming of the MV “Response Factor” should be programmed (based on the result of the sensor modulation after 6 minute walk; starting at nominal 8).
- The resulting HR frequency in the sensor response modulation (especially in the 2nd part of the 6 minute walk) should result in a minimum of 70% of APMHR so that an appropriate HR can be achieved during future exercises.

A screen shot for the pacing configuration is shown in Figure 11-2.

Figure 11-2: One Month Follow up Programming Screen

[figure not shown]

Table 11-7 provides an overview of the age dependent values as guidance for hall walk sensor adjustments to achieve optimal pacing rates, if clinically acceptable.

Table 11-7: Age Predicted Heart Rates (100%, 80%, 70%)

Age			APMHR	APMHR*80%	Programmed Value for APMHR*80%	APMHR*70%
55	to	59	165	132	130	116
60	to	64	160	128	130	112
65	to	69	155	124	125	108
70	to	74	150	120	120	105
75	to	79	145	116	115	101
80	to	84	140	112	110	98
85	to	89	135	108	110	95

APHR=age predicted heart rate, APMHR=age predicted maximal heart rate

MICS should be used for device interrogation. Events including (but not limited to) drop-outs during use of MICS, threshold test taking too long, loss of STAT Pace, etc. are required to be reported. The subject impact should be documented in the event description.

After final programming and sensor optimization, counters must be cleared and the final data interrogation can be saved for the clinical records as data file; the data does not need to be submitted as part of this study.

All current/concomitant heart failure medication classes, including changes to medications, are to be noted in the eCRF.

Details on the occurrence of any USADE, SADE, ADE, DD, SAE or device-related malfunction which have occurred since the previous visit are to be recorded.

Subjects will have their device performance, nominal alerts and diagnostic data downloaded remotely via the Latitude system by the BSC Latitude team during this visit timeframe. The subject device memory file will be collected. The following will be collected from the Latitude report by the core lab:

- Identify the atrial histogram. Report the “10 bpm bin” with **most paced beats by number** and report the %AP.
- Identify the atrial histogram. Report the “10 bpm bin” with **most sensed beats by number** and report %AS.

- HRS calculated from %AP and %AS.

11.8. 3 Month Clinic Visit (91 ± 21 days post-implant procedure; required)

Clinical assessments may be done at this visit, if the assessment is part of the center's SOC procedures.

The subject should have a vigorous 6 minute walk, to be done in the mode programmed at the 1 month follow up visit (e.g., DDDR for chronotropic incompetent patients and DDD for patients who clinically don't need rate adaptive pacing). Data to be collected in association with the walk include:

- age predicted heart rate
- heart rate prior to and at the conclusion of the walk
- maximum heart rate
- distance walked (in meters)
- any symptoms experienced.

MICS should be used for device interrogation. In case of but not limited to: e.g. drop-outs during use of MICS, or threshold test taking too long, loss of STAT Pace, etc. it is required to report all those events. The subject impact should be documented in the event description.

All subjects will be “interrogated” after the 6 minute walk test and the data must be saved prior to any re-programming.

The initial data interrogation the data file must be saved and stored in the subject binder. The file must be uploaded as a ZIP file into the study database.

If the HRS is still > 70 the response factor may be increased by 1.

A BiV-paced post-implant 10s programmer ECG recording is required to be uploaded to the study database for core lab review.

Subjects will have their device performance, nominal alerts and diagnostic data downloaded remotely via the Latitude system by the BSC Latitude team during this visit timeframe.

The final programming will be collected via the Latitude database and does not need to be uploaded.

The following will be collected from the Latitude report by the core lab:

- Identify the atrial histogram. Report the “10 bpm bin” with **most paced beats by number** and report the %AP.
- Identify the atrial histogram. Report the “10 bpm bin” with **most sensed beats by number** and report %AS.

- HRS calculated from %AP and %AS.

This visit is intended to evaluate the confidence interval (CI) using the HRS; confirm device diagnostics; and document subject symptoms. In particular all “trending” information should be noted. The BiV testing routine should document the PR interval over multiple intervals; RVS to LVS timing for each LV electrode; selection of final LV pacing/sensing vectors; use of Smart Delay to determine paced and sensed AV delays; and confirmation of LV-RV offset.

Output programming should be tested via LVAT and manually, the functionality of MICS confirmed and the PRM interface rating is to be documented. All daily measurement assessments should be confirmed manually.

All current/concomitant heart failure medication classes, including changes to those medications, are to be noted in the eCRF.

Details on the occurrence of any USADE, SADE, ADE, DD, SAE or device-related malfunction which have occurred since the previous visit are to be recorded.

11.9. Latitude based Close-out (91 - 120 days after the study is closed for enrollment; required)

Each subject will be followed up for 3 to 16 months (the maximum time in the study for any subject) following the implant procedure. Each subject should have a remote Latitude based Close-out (Latitude Report) collected within 3 to 4 months (91 - 120 days) after the date the study is closed to enrollment. All centers will be notified of this date. For subjects reaching 16 months, the Latitude based Close-out will be performed before reaching 16 months in the study, since 16 months is the maximum time in the study for any subject.

Subjects will not need to come to the study facility for any study procedures, but any clinical assessments done as part of center SOC should be documented on the eCRF.

During the remote Close-out, RV and LV pacing configuration and pacing threshold and battery voltage should be documented in the eCRF. Battery longevity will be monitored and documented. All device alerts will be reviewed and should correspond to the facility event reporting (e.g. SADE, ADE, SAE; DD for confirmed alert; or DD for false positive alert).

Subjects will have their device performance, nominal alerts and diagnostic data downloaded remotely from the Latitude BSC team during this visit timeframe.

Once the subject completes the Latitude based Close-out, participation in this study has been completed. In case of premature termination of the study, data collection will stop accordingly.

If a device-related event (USADE, SADE, ADE) is ongoing at the time of study completion, the subject may be asked to remain enrolled in the study and provide additional information regarding the event until the event is resolved. The physician will provide treatment for any ongoing events according to SOC regardless of whether the subject agrees to continue participating in the study.

11.10. Unscheduled or Interim Visits outside of Study Visit Windows

Should the subject be hospitalized or have an unscheduled or additional interim ambulatory/in clinic visit (e.g., related to center SOC, HF, resynchronization therapy, or antiarrhythmic therapy, or a visit with study personnel for any reason), the Investigator is responsible for notifying the sponsor. For Unscheduled Visits (outside of study visit schedule for any reason) an Unscheduled Follow-up eCRF should be completed in order to document this visit. The visit should be documented. If the visit was necessary due to an event which was serious or related to the device the Event-report eCRF must be completed. The occurrence of any event (USADE, SADE, SAE, ADE or DD, including but not limited to: drop-outs during use of MICS, threshold test taking too long, loss of STAT Pace, etc.) must be reported. The subject impact should be documented in the event description.

11.11. Source Documents

Table 11-8 summarises all source data requirements for this CIP. Most source documents will be filed in the subject's hospital chart since all procedures will follow SOC.

Some device measurements (e.g. 17 pacing vectors, 6 minute walk test, etc.) need to be documented on Worksheets which should be filed in the patient binder. Some source documents (e.g., 10s programmer ECG strips, device data memory file) will also be kept in the patient binder after the upload into the study database. Where copies of the original source document and printouts of original electronic source documents are retained, these shall be signed and dated by a member of the investigation study team (Research Coordinator or Investigator who is authorized per the delegation log). Other copies and measurements outside SOC as well as the patient consent form should be kept in the subject binder.

All personal information should be removed from all documents prior uploading into the study database and replaced by the study ID. In case this is not possible the database administrator will anonymize data as required.

Table 11-8: Source Documentation Requirements

Requirement	Disposition
Subject Consent Form	1-Retain subject file, 2-study binder, 3-Subject copy
Enrollment and Baseline Data	Retain in subject hospital file
Implant Measurement Worksheet	Subject binder
Implant Procedure Medical Records	Retain in subject hospital file
Pre-discharge Clinic Visit Data	Retain in subject hospital file and Subject binder
1 and 3 month Clinic Visit Data	Retain in subject hospital file and Subject binder
Interim and Unscheduled Visit Data	Retain in subject hospital file
Latitude report Close-out Data	Latitude database and pdf - Report in Study Database
Device Event Data	Retain in subject hospital file and report into the study database
Protocol (CIP) Deviation	Report in Study Database
Study Withdrawal Worksheet	Subject binder
12-lead ECG e-Recording	Retain in subject hospital file and copy upload to study database
10s Programmer ECG Recording	Subject binder, upload to study database
Device Interrogation and Print-outs	Retain in subject hospital file
6 minute walk test results documented on the worksheet	Retain in subject hospital file or in the subject binder
Latitude device and alert data	Latitude database and copy upload into study database

12. Statistical Considerations

12.1. Primary Safety and Effectiveness Endpoints

12.1.1. Primary Safety Endpoint

The primary safety endpoint for this study is to:

- evaluate and document the device-related complications by assessing the DRCFR at 3 months post-implant.

Safety will be evaluated by the DRCFR from implant through 3-months post-implant, based on complications that are related to the Ingenio 2 CRT-P device. A device-related complication is an AE that resulted in death, serious injury, a correction using invasive intervention or permanent loss of device functions, and that was assessed as related to the device. Device-related complications that may count against the primary safety endpoint are outlined in Section 18.1 and Section 18.2 of this CIP.

12.1.1.1. Hypotheses

The null and alternative hypotheses are as follows:

H_0 : The DRCFR from 0-3 months \leq 87.5%

H_A : The DRCFR from 0-3 months $>$ 87.5%

The null hypothesis (H_0) will be rejected if the lower one-sided 95% confidence bound for the DRCFR is greater than the performance goal of 87.5%.

12.1.1.2. Statistical Methods

When the final study subject reaches the 3 Month required follow-up visit, the primary safety analysis will be performed based on exact binomial methods for the estimation of the DRCFR, including the exact lower one-sided 95% confidence bound. Subjects that die/withdraw or are lost-to-follow-up prior to the 3-month endpoint evaluation ($\leq 91 + 21$ days post-implant or post-implant attempt) and have not experienced device-related complications will be excluded from the analysis. The sample size was adjusted to account for up to 20% attrition to ensure there would be a sufficient number of evaluable subjects through 3-months.

The primary safety endpoint will evaluate the DRCFR through 3-months post-implant (or implant attempt), calculated using exact binomial methods. The null hypothesis will be rejected and the endpoint considered met if the lower one-sided 95% confidence bound for the DRCFR at 3-months is greater than 87.5%.

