9.1. Study Population and Eligibility

Inclusion and Exclusion criteria are listed in Sections 9.2 and 9.3 below.

Subjects who are enrolled but later determined to not fulfill all inclusion and exclusion criteria after an attempted 3-lead device system implant will be considered to have incurred a Clinical Investigation Plan (CIP) deviation. These subjects will not be included in the planned data analysis but will be followed until the end of the study. Subjects who were intended to be implanted with a Visionist device, or who did not receive a Visionist device after an attempted implant should be withdrawn 30 days after the unsuccessful attempt if all pending events are closed. Once it has been

determined that a subject did not fulfill any inclusion/exclusion criteria, only observational data will be collected for that subject at any visit attended.

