9.3. Exclusion Criteria

Subjects who meet any one of the following criteria (Table 9-2) will be excluded from this clinical study.

Table 9-2: Exclusion Criteria

 1. Documented life expectancy of less than 12 months 2. Currently on the active heart transplant list 3. Enrolled in any other concurrent study without prior written approval from BSC, with the exception of local mandatory governmental registries and observational studies/registries that are not in conflict and do not affect the following: 
 o Schedule of procedures for the Rally CRT-P Study (i.e., should not cause additional or missed visits) o Rally CRT-P Study outcomes (i.e., involve medications that could affect the heart rate of the subject) o Conduct of the Rally CRT-P Study per Good Clinical Practice (GCP)/ International Standard Organization (ISO) 14155:2011/ local regulations as applicable 4. In chronic atrial fibrillation 5. Age predicted maximal heart rate (APMHR) needs to be programmed < 80% for clinical reasons at time of enrollment. 6. Not planned to receive a functional atrial lead 7. Per the implanting physician's discretion, subject is not a suitable candidate to receive the study device as determined during the implant procedure 8. Women of childbearing potential who are or might be pregnant at the time of study enrollment 9. Unwilling or unable to participate in all scheduled study follow up visits at an approved study center 10. Does not anticipate being a resident of the area for the scheduled duration of the trial.

10. Subject Accountability

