10.1. Point of Enrollment

Subjects will only be enrolled in this study if they meet all eligibility criteria and provide written informed consent. If a subject doesn't meet all eligibility criteria prior to the implant procedure (e.g., no attempt of Rally CRT-P implant is planned) the subject will be withdrawn from the study; any points of ineligibility must be clearly documented in the enrollment/screening log. These subjects will be considered consent ineligible as discussed in Section 10.3, and will not count towards the enrollment ceiling. Any subject that signs consent and meets all Inclusion Criteria and does not meet any Exclusion Criteria will be enrolled followed in the study. If a subject signs consent and meets all eligibility criteria but does not receive the Rally CRT-P implant (for example: anesthesia complications, Visionist CRT-P device was finally not implanted, etc.), the subject will be followed for 30 days for safety reasons and will then be withdrawn from the study (Section 9.1).

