12.4. General Statistical Methods

12.4.1. Analysis Sets

All subjects where implant with the Ingenio 2 CRT-P device was successful will be included in the primary endpoints analyses. For the DRCFR primary endpoint, subjects where the Ingenio 2 CRT-P device was attempted but not successfully implanted will also be included. Nevertheless, for the DRCFR primary endpoint, subjects that die/withdraw or are lost-to-follow-up prior to the 3-month endpoint evaluation (91 days post-implant or post-implant attempt) and have not experienced device-related complication will be excluded from the analysis.

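### The primary safety analysis set is defined inconsistently: two exclusion cut-offs, failed attempts that can hardly count as successes, and no agreed rule for subjects found ineligible after an attempt

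*Combined protocol and SAP*

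**What the plan says.** **Cut-off.** Section 12.1.1.2 removes subjects who die, withdraw or are lost before the 3-month evaluation "and have not experienced device-related complications will be excluded from the analysis". It puts the limit at 91 + 21 days after implant or implant attempt. Section 12.4.1 repeats the rule for those who leave "prior to the 3-month endpoint evaluation (91 days post-implant or post-implant attempt"), without the 21 days.

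**Failed attempts.** Section 12.4.1 states that, for the DRCFR, "subjects where the Ingenio 2 CRT-P device was attempted but not successfully implanted will also be included". Section 9.1 says that such subjects "should be withdrawn 30 days after the unsuccessful attempt if all pending events are closed". Under Section 10.1, for a subject who does not receive the implant, "the subject will be followed for 30 days for safety reasons and will then be withdrawn from the study". Table 25-2 requires 30 ± 7 days of follow-up after an attempt.

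**Eligibility.** For subjects found ineligible after an attempted implant, Section 9.1 says "These subjects will not be included in the planned data analysis but will be followed until the end of the study". Section 10.3 places the actively enrolled, meaning eligible and consented, subjects in the analysis. Section 12.4.1 says "All subjects where implant with the Ingenio 2 CRT-P device was successful will be included in the primary endpoints analyses", and adds the failed attempts for the DRCFR, with no eligibility condition. Exclusion criterion 7 applies when, in the implanting physician's judgement, the "subject is not a suitable candidate to receive the study device as determined during the implant procedure".

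**The concern.** The primary safety verdict rests on about 50 to 60 subjects and a handful of complications, so the plan should fix in advance who is counted. It leaves three points open.

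- A subject who leaves without a complication on days 91-112, with no 3-month visit, is excluded under Section 12.1.1.2 and kept under Section 12.4.1.
- A failed attempt is in the analysis set by name. Because follow-up ends at about 30 days and the exclusion also runs from the attempt, a complication-free attempt is then excluded as a withdrawal, while an attempt with a device-related complication stays as a failure. The narrow exception is an attempt kept beyond 30 days because an event is still pending.
- A subject found ineligible after an attempt is out under Section 9.1 and not excluded by Section 12.4.1. Because exclusion 7 is judged during the procedure, a failed attempt could be classed as ineligible and removed together with its complication.

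The conflicts do not all push the same way. Losing complication-free subjects can turn a pass into a miss; losing an ineligible subject who had a complication can turn a miss into a pass. The study is open-label and single-arm, so a choice made late could be made with the complications known.

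**Working it through.** **Inputs** (Sections 12.1.1 and 12.3): performance goal 87.5%, expected DRCFR 97.5%, one-sided alpha 0.05, power 80%, attrition up to 20%, 49 subjects for analysis, 62 enrolled. The endpoint is met if the exact one-sided 95% lower bound exceeds 87.5%.

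**1. The plan's own figure.** For each n, take the largest number of failures f with P(at least n − f complication-free | 0.875) ≤ 0.05, then compute the power at 0.975.
- n = 49: f = 2, exact alpha 0.0461, power 87.6%.
- n = 48: f = 1, exact alpha 0.0129, power 66.2%.
- 49 / (1 − 0.20) = 61.25, rounded up to 62.

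The stated 49 and 62 are reproduced.

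**2. The steps.** The most failures that still meet the goal are 3 for n = 60-62, 2 for n = 49-59 and 1 for n = 37-48. With x complication-free among n, the exact (Clopper-Pearson) lower bound is the 5th percentile of Beta(x, n − x + 1):

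| Complication-free / n | Lower bound | Goal met? |
|---|---|---|
| 57/60 | 87.58% | yes |
| 56/59 | 87.38% | no |
| 47/49 | 87.70% | yes |
| 46/48 | 87.46% | no |
| 58/62 | 85.84% | no |
| 58/61 | 87.78% | yes |

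The first two pairs differ by one complication-free subject, kept or excluded. The last pair differs by one subject with a complication, kept or removed.

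**3. Cut-off conflict.** Assume one complication-free exit on days 91-112 and a true rate of 97.5%. The two sections disagree only if the number of complications among the others is exactly the one that the step affects.
- 60 v 59: P(3 complications among 59) = C(59,3) × 0.025³ × 0.975⁵⁶ = 0.123.
- 49 v 48: P(2 complications among 48) = C(48,2) × 0.025² × 0.975⁴⁶ = 0.220.
- Every other n from 49 to 62: 0, because the permitted number of failures is the same at n and n − 1.

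**4. Failed attempts.** The documents give no expected number, so 1 to 5 are assumed among 62, with a 2.5% complication risk and no other attrition. Let A be the number of attempts, X ~ Bin(62 − A, 0.025) the complications in implanted subjects and C ~ Bin(A, 0.025) those in attempts. As written, the estimate is 1 − (X + C)/(62 − A + C).
- Mean estimate: 97.46% for A = 1, falling to 97.29% for A = 5. The bias is −0.04 to −0.21 points, against the device.
- Verdicts that differ from keeping every attempt: 0% for A = 1 or 2, 11% for A = 3, 13% for A = 5. Most of this comes from crossing the 60/59 step.

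**5. Eligibility conflict.** Assumed numbers of ineligible subjects, 2.5% risk each. Opposite verdicts arise in 0.3%, 0.6% and 11.5% of trials for 1, 2 and 3 such subjects at n = 62. For one such subject the figure is 12.0% at n = 60 and 21.5% at n = 49. The change from 58/62 to 58/61 is therefore possible but rare: it is the 0.3% case.

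**The case against.** **The two cut-offs describe one visit.** Both sections refer to the 3-month evaluation; one gives its nominal day and the other the end of its window. That may explain the difference, but a program needs one day, and the two days classify a late exit differently. It is fair that the conflict matters at only two steps, and that 48 or 49 evaluable subjects of 62 means losing 14 or 13, slightly beyond the planned 20%.

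**Attempts are an inclusion followed by an express exception.** This is correct as a matter of reading, and the bias is small and conservative. What stands is that, given withdrawal at about 30 days, the exception removes nearly every attempt that could count as a success.

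**Section 12.4.1 is only silent on eligibility.** Sections 9.1 and 10.3 do point the same way. But Section 12.4.1 is the section that defines the analysis sets, and it speaks of all successful implants. The route through exclusion 7 is a possibility that the wording leaves open, not something that the plan intends; Section 10.1 separately covers eligible subjects who end up without the device.

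**Stronger readings that the documents do not support.** A reader might treat the synopsis, which speaks of actively enrolled subjects and mentions no exclusion, as a further contradiction. It refers to Section 12 for the details and does not say that leavers count as successes. A reader might also infer that excluding complication-free leavers inflates the type I error. That needs leavers with a much higher complication risk that mostly goes unseen, and the documents give no figure for either.

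**Conclusion.** The concern holds as an inconsistency in the definition of the primary safety analysis set. The cut-off and eligibility statements conflict in the current text; the handling of attempts conflicts in its effect. One subject can change the verdict, but only near a step. For a single complication-free exit on days 91-112 at a true rate of 97.5%, that is about 12% of trials at 60 v 59, 22% at 49 v 48, and 0% at every other n from 49 to 62. The effect of the attempt rule on the estimate is at most about 0.2 points against the device. The eligibility conflict is the one that can favour the device. The numbers of late exits, attempts and ineligible subjects are assumptions, because the documents do not give them. The sample size of 49 for analysis and 62 enrolled is correct and unaffected. The plan should be corrected before the primary analysis.

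**What to change.** Keep the exact binomial test and settle the following before the primary analysis.

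- **One exclusion rule,** worded identically in Sections 12.1.1.2 and 12.4.1: a subject who dies, withdraws or is lost without a device-related complication is excluded only if the exit came by day 112 and before the 3-month visit was done. Subjects still in the study who miss or delay the visit stay in.
- **One denominator:** subjects implanted or attempted. Subjects classed as intent in Table 25-2, who have no implant procedure, are out. Align the synopsis wording.
- **One eligibility rule** in Sections 9.1 and 12.4.1 for subjects found ineligible after an attempt, applied without regard to complications, with exclusion-7 cases classed as attempts. Report the opposite choice as a sensitivity analysis.
- **Symmetric handling of attempts:** an attempt that completes its planned 30-day follow-up without a device-related complication counts as complication-free. Report the result with all attempts removed as a sensitivity analysis.

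Best-case and worst-case counts for early leavers are an optional addition.

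The cost is wording in a few sections and a few lines of code; the dates needed are already collected. The downside is that attempts then count on 30 days of follow-up rather than 3 months, which the report should say.
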